12.2.3.3 Regulatory Reporting Requirements for SAEs

The Sponsor or Sponsor representative will report fatal or life-threatening SAEs that are unexpected suspected adverse reactions to the relevant regulatory authorities within 7 calendar days, and non-fatal or life-threatening SAEs that are unexpected suspected adverse reactions within 15 calendar days as Investigational New Drug (IND) Safety Reports, in accordance with 21 CFR 312.32. Prompt notification of SAEs by the Investigator to the appropriate project contact for SAE receipt is essential so that legal obligations and ethical responsibilities towards the safety of other patients are met.

12.2.3.4 Reporting Safety Information to the IRB/IEC

The Investigator, or responsible person according to local requirements, will comply with the applicable local regulatory requirements related to the reporting of SAEs to the Institutional Review Board (IRB)/Independent Ethics Committee (IEC).

All Investigators involved in studies with this drug will receive a copy of each IND Safety Report. When an Investigator receives an IND Safety Report or other safety information (e.g., revised Clinical Investigator's Brochure/Investigator's Brochure), the responsible person according to local requirements is required to promptly notify his or her IRB/IEC.

12.2.4 Follow-up of Adverse Events

The Investigator is required to proactively follow each patient and provide further information regarding AEs and SAEs. All AEs and SAEs will be followed until 30 (+4) days after the last dose of study drug, resolution of the event, until the condition stabilizes, until the event is otherwise explained, or until the patient is lost to follow-up, whichever occurs earlier. Once resolved, the appropriate CRF entries and event reporting forms will be updated, as appropriate.

All AEs and SAEs documented at a previous visit/contact and designated as ongoing will be reviewed at subsequent visits/contacts. The Investigator will ensure that follow-up includes any supplemental investigations as may be indicated to elucidate the nature and/or causality of the AE or SAE. This may include additional laboratory tests or investigations, histopathological examinations, or consultation with other health care professionals.

The Sponsor or the Sponsor's designee may request that the Investigator perform or arrange for the conduct of supplemental measurements and/or evaluations to elucidate as fully as possible the nature and/or causality of the AE or SAE. The Investigator is obligated to assist. If a patient dies during participation in the study or during a recognized follow-up period, the Sponsor will be provided with a copy of any post-mortem findings, including histopathology.

New or updated information will be recorded on the originally completed SAE forms, with all changes signed and dated by the Investigator. This information will also be entered into the CRF.

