7.1.2 Double Blind Treatment Phase

The total duration of the double-blind Treatment Phase will be approximately 6 months (i.e., 168 days, consisting of six 28-day treatment cycles).

Eligible patients, stratified as to the presence or absence of tophi, will be randomized in a 1:1:1 allocation ratio prior to Baseline to receive one of two dose levels of SEL-212 or placebo. The SEL-212 doses will differ as to the SEL-110.36 component. Participants will receive SEL-037 administered at a dose level of 0.2 mg/kg via intravenous (IV) infusion immediately after receiving SEL-110.36 at a dose level of either 0.1 mg/kg (SEL-212A) or 0.15 mg/kg (SEL-212B) via IV infusion. The placebo will consist of normal saline that will be administered in the same way that the SEL-212 components are administered to maintain the integrity of the study blind. Refer to [Section 10](#) for details about study drug administration.

Patients will complete 6 treatment periods each having a duration of 28 days. Patients will receive treatment with study drug or placebo on Day 0 of each treatment period for a total of 6 doses. For each treatment cycle, patients in both treatment and placebo groups will receive premedication to minimize the potential for infusion reactions during study drug administration. After completing the study drug infusions, participants will remain at the investigational site for 1 hour for safety assessments.

With each dose, a blood sample will be drawn for assessment of sUA level and uricase activity immediately prior to infusion (i.e., Time 0 h) with SEL-212 or placebo and 1 hour after the infusion of the second component of SEL-212 or of placebo is completed. Serum uric acid levels will be assessed through additional post-infusion blood samples at pre-determined time points by an independent, central, unblinded medical monitor.

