Gout flares will be assessed at each study visit during the Treatment Phase using a validated definition of flares in patients with established gout ([Gaffo 2018](#)). In addition, in an exploratory manner, gout flares will be self-assessed by the patient weekly after randomization and in each Treatment Period using a weekly flare diary ([Poiley 2016](#)). Patient reported outcome measures (PROs), tophus burden and joint swelling and tenderness will be assessed on Day 0 of Treatment Periods 1 and 4, and at the end of Treatment Period 6 or early termination (ET) if a patient discontinues the study prior to the end of 6 monthly infusions. Samples for anti-uricase, anti-PEG, and anti-pegadricase antibody levels will be taken (i) prior to administration of study drug dosing and at Day 21 for each of the six treatment periods throughout the trial and (ii) at the end of Treatment Period 6 or at ET. Exploratory assessments of inflammatory/immunologic biomarkers and multiomic analysis will also be assessed.

[figure not shown]
Safety laboratory samples, consisting of, but not limited to, complete blood count (CBC) including white blood cell count (WBC) and absolute neutrophil count; liver function tests (LFTs) including aspartate aminotransferase (AST) and alanine transaminase (ALT); serum lipids (including triglycerides and low density lipoprotein (LDL)), analyses of renal function including creatinine, urine albumin creatinine ratio (UACR), and estimated glomerular filtration rate (eGFR) will be collected on Day 0 and Day 21 of Treatment Period 1, on Day 21 only of each of Treatment Periods 2-5, and on Day 21 and Day 28 / ET of Treatment Period 6. On Treatment Period 1 Day 0, safety laboratory samples will be collected pre-infusion in both the SEL-212 arm and the placebo arm. Concomitant medications and procedures and adverse events (AEs) will be monitored continuously during the study. Post-Baseline chest X-rays (CXR) will be taken at six months / ET to assess for presence of or changes in interstitial lung disease (ILD) compared to baseline CXR.

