12.1.8.10 Pregnancy Screen

Samples for urine pregnancy testing (hCG) will be obtained.

Male patients of reproductive potential who are having intercourse with female partners of childbearing potential must agree to use 2 forms of contraception, 1 of which must be a barrier method, during the study and for 4 months after the last study drug administration. Acceptable barrier methods include a condom and diaphragm. Acceptable forms of birth control for female partners of childbearing potential are non-hormonal and hormonal intrauterine devices, hormonal birth control pills, hormonal birth control patches, hormonal birth control injections, hormonal birth control implants. Spermicide used alone is not an acceptable method and must be used with another acceptable form birth control method. Abstinence is acceptable if consistent with the patient's normal lifestyle.

Female patients are required to have negative hCG test results throughout the study. If a female patient becomes pregnant after she begins taking study drug, the procedures in [Section 12.2.2.7](#) should be followed.

In addition, for any reported case of delayed menstrual period (over 1 month between menstruations) and for those women with infrequent or irregular menstrual cycles, confirmation of absence of pregnancy should occur.

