12.2.2.6 Laboratory and Diagnostic Abnormalities as Adverse Events

Clinically significant abnormal laboratory findings or other abnormal diagnostic assessments (e.g., ECGs, vital signs) that are detected in dosed patients or that significantly worsen relative to baseline in dosed patients will be reported as AEs. Clinical significance is based on the Investigator's judgment but will typically include findings that result in study withdrawal, result in active management of the patient, or are associated with clinical signs and symptoms. Since the study requires patients with elevated or abnormal sUA levels, abnormal sUA levels will typically not be an AE unless judged by the Investigator as being more severe than expected for the patient.

12.2.2.7 **Pregnancy**

While pregnancy itself is not considered to be an AE, any pregnancy complication or elective termination of a pregnancy for medical reasons will be recorded as an AE and followed. The outcome of all pregnancies must be followed up and documented even if the patient is no longer a study patient.

The Investigator, or his/her designee, will collect pregnancy information on every female who becomes pregnant while enrolled in this study and on every female partner of a male patient who becomes pregnant while the male partner is enrolled in this study. The Investigator will report to the Sponsor or Sponsor's designee within 24 hours of learning of a patient's or female partner of a patient's pregnancy. In the case of a female partner of a male participant enrolled in the study becoming pregnant while the male patient is enrolled in this study, a separate pregnancy partner informed consent form will be completed by the patient's partner. The patient or female partner of a patient must also be followed to determine the outcome of the pregnancy. Information on the status of the mother and child will be forwarded to the Sponsor or Sponsor Designee, as appropriate. Follow-up on the child will be to the first well-child visit. Any premature termination of the pregnancy will be reported.

A spontaneous abortion or congenital abnormalities/birth defects will be considered SAEs and will be reported as such. Furthermore, any SAE occurring as a result of a post-study pregnancy and is considered reasonably related to the study drug by the Investigator, will be reported to the Sponsor.

12.2.3 **Reporting Adverse Events**

12.2.3.1 **Adverse Event Reporting Period**

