Appendix A Schedule of Assessments, continued

Assessment	Scr. - 45 d to D0 (Pre-dose) ³	Treatment Phase														EOS ¹	ET
		TP1 ²		TP2 ²		TP3 ²		TP4 ²		TP5 ²		TP6 ²					
Day	D0	D21	D0 ⁵	D21	D0 ⁵	D21	D0 ⁵	D21	D0 ⁵	D21	D0 ⁵	D7 ⁴	D14 ⁴	D21 ⁴	D28		
Tophus Assessment/Photography	X							X								X	X
Gout Flare Assessment ²²	X	X	X	X	X	X	X	X	X	X	X	X	X	X	X	X	X
Gout Flare Weekly Diary		Continuously on Weekly Basis ²³															X
Joint Assessment (tenderness, swelling)		X						X								X	X
Health Questionnaires ²⁴		X						X								X	X
Collect Sample for sUA	X	Refer to Schedule of Assessments (Appendix B) for sUA Sample Collection during Treatment Phase															X
PD/Uricase Activity Assessment		Refer to Schedule of Assessments (Appendix B) for PD/Uricase Activity Assessments during Treatment Phase															X
Study Drug Administration		Refer to Schedule of Assessments in Appendix B for Study Drug Administration during the Treatment Phase															
Infusion Reaction Follow-up		Refer to Section 12.2.1.5															
Concomitant Medications / Procedures		Continuously														X	X
AE Collection		Continuously														X	X
SAE Collection		Continuously														X	X

1. Phone call at 30 (+4) days after the last study drug infusion for assessment of concomitant medications/procedures, AEs, and SAEs.
2. Visit window at Day 21 of each Treatment Period is +2/-1 days; visit window at Day 7 and Day 14 of Treatment Period 6 is +2/-1 days; visit window at Day 28 of Treatment Period 6 is +3/-4 days.
3. Visit window is -2 days.
4. Assessments at this visit are permitted to be performed remotely (inclusive of collecting applicable lab draws and assessments per protocol visit windows).

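### Required follow-up of open SAEs and AESIs ends 30 (+4) days after the last dose: nominally 2 to 6 days after the final X-ray and labs for patients given dose 6, and 22 to 138 days before that visit for patients withdrawn from drug earlier

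*Protocol*

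**What the plan says.** **Follow-up rule.** Protocol Section 12.2.4 reads "All AEs and SAEs will be followed until 30 (+4) days after the last dose of study drug, resolution of the event". It then adds stabilization and another explanation as end points and closes with "or until the patient is lost to follow-up, whichever occurs earlier". That makes five end points, of which the first to occur ends follow-up. The rule covers every AE and SAE without distinction.

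**Last scheduled safety assessments.** Section 7.1.2 says "Post-Baseline chest X-rays (CXR) will be taken at six months / ET to assess for presence of or changes in interstitial lung disease", and Appendix A schedules no other post-baseline film. The last safety labs are at TP6 Day 21 and TP6 Day 28 or early termination. By Appendix A, footnote 2, the "visit window at Day 28 of Treatment Period 6 is +3/-4 days". The only later contact is the end-of-study call, described in footnote 1 as "Phone call at 30 (+4) days after the last study drug infusion". It covers concomitant medication and adverse events, not labs or imaging.

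**Patients withdrawn from study drug.** Section 7.1.3 keeps them attending visits to the end of TP6, and Appendix A marks AE collection as continuous. Section 12.2.3.1 nevertheless ends AE reporting 30 (±1) days after the last infusion, and Section 12.2.4 ends follow-up 30 (+4) days after the last dose.

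**Pregnancy, under a different rule.** Section 12.1.8.10 requires contraception by male patients of reproductive potential whose partners can conceive, "during the study and for 4 months after the last study drug administration". Section 12.2.2.7 collects information "on every female partner of a male patient who becomes pregnant while the male partner is enrolled in this study".

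**The concern.** The AESI list in Section 12.2.1.5 includes interstitial lung disease (ILD), malignancy, thrombosis, infection and, when clinically significant, worsening renal function, proteinuria and leukopenia. Several of these would not be expected to settle within days. The X-ray meant to detect ILD is taken at the visit closest to the follow-up limit. An event found there and still open at the cap has no required follow-up to outcome, so the trial may be unable to say whether late-detected toxicity was reversible.

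Patients withdrawn from drug raise a second problem. The protocol keeps examining them to the end of TP6, while its AE reporting and follow-up limits run from the last dose and can lapse well before the final X-ray and labs. The efficacy analysis is not affected; what suffers is the completeness of the safety record.

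**Working it through.** **Timeline check.** Section 7.1.2 gives "168 days, consisting of six 28-day treatment cycles". Taking the first dose as study day 0, the TP6 dose is at 5 × 28 = day 140 and TP6 Day 28 is at day 168. Section 7.1 states a maximum participation of 215 days: 45 days of screening + 140 + 30 = 215, so the stated figure is reproduced. The stated minimum of 184 needs 14 days of screening (14 + 140 + 30); the 7-day minimum washout would give 177. Nothing below rests on the minimum.

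**Patients given dose 6.** Follow-up left = cap day − visit day, both counted from the TP6 dose.
- Nominal visit, Day 28: 30 − 28 = 2 days to 34 − 28 = 6 days.
- Extremes of the visit window (Day 24 to Day 31): 30 − 31 = −1 day to 34 − 24 = 10 days.
- With the 30 (±1) reporting limit of Section 12.2.3.1 instead: 29 − 28 = 1 day to 31 − 28 = 3 days.

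**Patients withdrawn earlier.** With the last dose in TP k, the dose is on study day 28(k − 1) and the cap is 30 to 34 days later. The shortfall is 168 minus the cap.

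| Last dose | Study day of dose | Cap (study day) | Days from cap to TP6 Day 28 |
|---|---|---|---|
| TP5 | 112 | 142–146 | 22–26 |
| TP4 | 84 | 114–118 | 50–54 |
| TP3 | 56 | 86–90 | 78–82 |
| TP2 | 28 | 58–62 | 106–110 |
| TP1 | 0 | 30–34 | 134–138 |

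**Pregnancy collection.** Taking 4 months as 120 days, a patient given dose 6 is enrolled until Day 30 to 34 (Section 8.3.2). The uncovered time is 120 − 34 = 86 to 120 − 30 = 90 days, or 72% to 75%. If the last dose was earlier, enrolment to study day 168 covers more of the period:
- TP5: 168 − 112 = 56 days covered, 64 uncovered (65.75 if 4 months is 121.75 days), about 2.1 to 2.2 months.
- TP4: 84 covered, 36 uncovered, about 1.2 months.
- TP3: 112 covered, 8 uncovered, about 0.3 months.
- TP2 or TP1: 140 or 168 covered, so no gap.

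**The case against.** The strongest reply is that the protocol does not close the file at Day 30 to 34, and much of it stands.

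- Section 12.2.4 also calls for supplemental investigations as indicated and obliges the investigator to assist when the sponsor asks for more. Ongoing events are reviewed at later visits and contacts, which partly helps patients withdrawn from drug because they still have visits.
- Section 12.2.2.2 lets causality be revised when new information arrives. Section 12.2.3.2 requires SAE follow-up information to be passed on promptly after receipt. Section 12.2.3.1 requires notification of related SAEs learned of after discharge.
- Safety labs are also drawn at Day 21 of every period, including TP6. The lab part of the point is therefore limited to abnormalities that first appear in the final week; the X-ray part is stronger.

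A reader might infer that outcome and causality are frozen at the cap. These clauses do not support that. What they lack is a default: none sets a later end date, Section 12.2.3.1 says investigators need not look for events in former patients, and its post-discharge clause does not reach non-serious AESIs.

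Two stronger readings of the pregnancy rules also fail. One is that the earliest-end-point wording of Section 12.2.4 causes the gap; it does not, because the limit lies in Section 12.2.2.7. The other is that partner pregnancies go wholly uncollected. Section 12.2.2.7 turns on when the partner conceives, follows the outcome of every pregnancy even after the patient has left, and requires reports of drug-related SAEs from post-study pregnancies. Nor does the 95.9% male share in the Phase 2 comparison (Section 7.6.3.2.2) make this a matter for nearly everyone, since the contraception rule covers only men of reproductive potential with partners who can conceive.

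**Conclusion.** The point holds for Section 12.2.4. An SAE or AESI that is open 30 (+4) days after the last dose has no required follow-up to outcome. For patients given dose 6, that leaves nominally 2 to 6 days after TP6 Day 28, and -1 to 10 across the windows. For patients withdrawn earlier, the last-dose limit lapses 22 to 138 days before that visit. This conflicts with their continued visits and AE collection.

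These figures assume that the six-month X-ray is taken at TP6 Day 28 (the end-of-study contact is a call), that no treatment period is extended, and that withdrawn patients reach TP6 Day 28 on schedule. The pregnancy gap is a separate, low-priority matter, confined to the group named in Section 12.1.8.10. It is about 86 to 90 of 120 days after dose 6 and shrinks to zero for earlier last doses.

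**What to change.** 1. In Section 12.2.4, keep the 30 (+4) day limit only for non-serious AEs that are neither AESIs nor drug-related. For SAEs, AESIs and drug-related AEs, delete it, so that follow-up runs to resolution, stabilization, another explanation or loss to follow-up.
2. Reconcile the 30 (±1) day limit in Section 12.2.3.1 with the 30 (+4) days in Section 12.2.4 and Appendix A, footnote 1. Reconcile both with continued visits and AE collection to the end of TP6 for patients withdrawn from drug, and with Section 12.2.1.1, which ties AE collection to the End of Study Visit.
3. Separately, amend the partner clause of Section 12.2.2.7 (not the neighboring clause on female patients) so that its collection period matches the contraception period stated in Section 12.1.8.10.

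**Cost.** A protocol amendment needs investigator signatures and IRB/IEC approval (Section 15.3) at about 50 centers. Some patients will need post-study follow-up. A telephone call may be enough for many events, but whether ILD or renal decline reversed needs a film or a lab result. The documents do not give the number of open events, and the AESI list includes gout flares and infections; the four remaining end points bound the workload. Database lock need not wait, because late outcomes can go through the safety database.

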13. STATISTICS

Details of the statistical methods outlined in the protocol for this study, including the hierarchical ordering of the secondary endpoints, will be documented in a Statistical Analysis Plan (SAP), which will be finalized prior to database lock. The SAP may add additional exploratory analyses; modifications to the planned analyses will be identified as such in the final SAP.

13.1 Sample Size Determination

The primary efficacy criterion in this study is defined as the percentage of the patients who achieve and maintain reduction of sUA < 6 mg/dL for at least 80% of the time during Treatment Period 6 by Day 28.

The sample size estimation is based on the main estimand for the primary efficacy criterion from version 5.0 of the protocol. This estimand considered all patients who discontinue study treatment due to lack of efficacy (e.g., meeting stopping rule), due to treatment-related or non-treatment related AE as treatment failures, as well as initiating prohibited medication that lowers sUA, withdrawal of consent or lost to follow up for reasons other than COVID-19.

Based on the results in the Phase 2 study (SEL-212/201) with SEL-212, the responder rate in all randomized and dosed patients is assumed to be 45% in SEL-212. For placebo, a responder rate of 5% is assumed. Considering a randomization ratio of 1:1:1 for SEL 212A and SEL-212B against placebo, a statistical power of 90%, a two-sided alpha-level of 2.5% and using the Chi-square test with continuity correction for the 2 pairwise comparisons of each SEL-212 dose group against placebo, 32:32:32 randomized and dosed patients will be required for each treatment group. Considering the potential that some randomized patients will terminate early (approx. 8%), the number of the patients required to be randomized and dosed in total is 105 (i.e., 35:35:35) to demonstrate efficacy. For the sample size estimation, the Chi-square test is used instead of the Mantel-Haenszel test, although the randomization will be stratified for tophus presence (yes/no), as there is no valid assumption of the distribution of this stratification variable within the eligible patient population.

From an amendment in version 6.0 of the protocol, the main estimand for the primary efficacy criterion was updated to include patients who present a positive COVID-19 test along with severe or critical symptoms of COVID-19, and patients who missed all assessments of sUA during Treatment Period 6, as treatment failures. In addition, the ongoing conflict between Ukraine and Russia may lead to treatment discontinuations and/or loss to follow-up in both countries; under the main estimand for the primary endpoint, these may be considered as treatment failures. As both these factors are expected to be unrelated to the treatment then assuming that the number of additional treatment failures to each arm would be roughly equal, the difference in response rates can still be assumed to be 40%, unless the treatment failure rate due to positive COVID-19 tests along with severe or critical symptoms of COVID-19 and treatment discontinuation/loss to follow-up due to the conflict between Ukraine and Russia is sufficiently high that a difference of 40% cannot be observed (i.e. the treatment failure rate in the active arms is >60%, so even if the responder rate for the placebo group is 0%, a difference of 40% cannot be observed).

To mitigate this risk, an additional 15 patients have been added to the study sample size to account for potential treatment discontinuations that may occur due to the ongoing COVID-19 pandemic as a result of the emergence of COVID-19 variants which were not accounted for in the sample size calculations. Furthermore, an additional 20 patients have been added to the original study sample size to account for the treatment discontinuations/loss to follow-up due to the conflict between Ukraine and Russia. These two additions to the sample size from the original sample size calculation results in approximately 140 patients (i.e., approximately 47 per group) to be randomized and dosed to demonstrate efficacy. This controls the power of each comparison vs. placebo at approximately 90%, even if the placebo arm were to be unaffected with respect to response probability by the conflict between Ukraine and Russia, with a response percentage of 5%, and the active treatment arm response percentage were to drop to 37%.

Sample size calculations were performed with the software package nQuery 8, Version 8.5.0.0 and updated using R software version 4.0.4.

